### 5.2 Secondary Endpoints

The following secondary endpoints will be evaluated:

- Major vascular complications through discharge
- Valve migration or embolization through discharge

## 6 STUDY POPULATION

The study population will be comprised of subjects with symptomatic, severe, calcific AS requiring AVR who are at intermediate operative risk and have appropriate iliofemoral anatomy for transfemoral access.

### 6.1 Inclusion Criteria

Candidates must meet all of the following criteria to be included in the study:

1. Severe, calcific AS meeting the following transthoracic echocardiogram (TTE) criteria:
  - Aortic Valve Area (AVA)  $\leq 1.0 \text{ cm}^2$  OR AVA index  $\leq 0.6 \text{ cm}^2/\text{m}^2$
  - Jet velocity  $\geq 4.0 \text{ m/s}$  OR mean gradient  $\geq 40 \text{ mmHg}$
2. New York Heart Association (NYHA) functional class  $\geq \text{II}$
3. Judged by the Heart Team to be at intermediate risk for open surgical therapy (i.e., predicted risk of surgical mortality  $\geq 3\%$  and  $< 8\%$  at 30 days, based on the STS risk score and other clinical co-morbidities unmeasured by the risk calculator)
4. The subject has been informed of the nature of the study, agrees to its provisions and has provided written informed consent as approved by the Institutional Review Board (IRB)/Ethics Committee (EC) of the respective clinical site.

## 6.2 Exclusion Criteria

Candidates will be excluded from the study if any of the following conditions are present:

1. Native aortic annulus size unsuitable for available THV sizes based on 3D imaging analysis
2. Aortic valve is unicupid, bicuspid or non-calcified
3. Pre-existing mechanical or bioprosthetic valve in any position. (Of note, mitral ring is not an exclusion)
4. Severe aortic regurgitation (> 3+)
5. Severe mitral regurgitation (> 3+) or  $\geq$  moderate stenosis
6. Ventricular dysfunction with left ventricular ejection fraction (LVEF)  $<$  30%
7. Cardiac imaging (echocardiography, CT and/or magnetic resonance imaging (MRI)) evidence of intracardiac mass, thrombus or vegetation
8. Evidence of an acute myocardial infarction (MI)  $\leq$  30 days before the valve implant procedure
9. Subjects with planned concomitant ablation for atrial fibrillation
10. Hypertrophic cardiomyopathy with obstruction (HOCM)
11. Coronary anatomy that increases the risk of coronary artery obstruction post-TAVR
12. Complex coronary artery disease (CAD):
  - a. Unprotected left main coronary artery
  - b. SYNTAX score  $>$  32 (in the absence of prior revascularization)
  - c. Heart Team assessment that optimal revascularization cannot be performed
13. Iliofemoral vessel characteristics that would preclude safe placement of the introducer sheath
14. Significant abdominal or thoracic aortic disease that would preclude safe passage of the delivery system
15. Active bacterial endocarditis within 180 days of the valve implant procedure
16. Stroke or transient ischemic attack (TIA) within 90 days of the valve implant procedure
17. Symptomatic carotid or vertebral artery disease or successful treatment of carotid stenosis within 30 days of the valve implant procedure
18. Severe lung disease (Forced Ejection Volume 1 (FEV1)  $<$  50% predicted) or currently on home oxygen
19. Severe pulmonary hypertension (e.g., pulmonary artery systolic pressure  $\geq$  2/3 systemic pressure)
20. Hemodynamic or respiratory instability requiring inotropic support, mechanical ventilation or

mechanical heart assistance within 30 days of the valve implant procedure

21. History of cirrhosis or any active liver disease
22. Renal insufficiency (estimated glomerular filtration rate (eGFR) < 30 mL/min per the Cockcroft-Gault formula) and/or renal replacement therapy at the time of screening
23. Leukopenia (WBC < 3000 cell/mL), anemia (Hgb < 9 g/dL), thrombocytopenia (Plt < 50,000 cell/mL), history of bleeding diathesis or coagulopathy or hypercoagulable states
24. Inability to tolerate or condition precluding treatment with antithrombotic therapy during or after the valve implant procedure
25. Absolute contraindications or allergy to iodinated contrast that cannot be adequately treated with pre-medication
26. Significant frailty as determined by the Heart Team (after objective assessment of frailty parameters)
27. Subject refuses blood products
28. Body mass index (BMI) > 50 kg/m^2
29. Estimated life expectancy < 24 months
30. Positive urine or serum pregnancy test in female subjects of childbearing potential
31. Currently participating in an investigational drug or another device study. Note: Trials requiring extended follow-up for products that were investigational, but have since become commercially available, are not considered investigational trials. Observational studies are not considered exclusionary.

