**Clinical Laboratory Tests:**

- White blood cell count (WBC), Hemoglobin, Platelet count
- Prothrombin Time (PT) or International Normalized Ratio (INR)
- Creatine Kinase (CK) and/or Troponins  $\leq$  72 hours before the valve implant procedure
- Creatinine (including calculation of eGFR per the Cockcroft-Gault formula)
- Albumin (as part of Frailty Index), total bilirubin
- Aspartate Aminotransferase (AST), Alanine Aminotransferase (ALT) – only for subjects with chronic liver disease
- Pregnancy test (urine or serum) – only for female subjects of childbearing potential

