### 10.2 Sample Size Considerations

The success criterion for this study is procedural success of at least 90%. The primary statistical analysis for this study is to estimate the procedure success rate. With a sample size of at least 55 subjects, if the observed rate is at least 90%, the lower bound of the observed 95% CI (calculated from binomial distribution) will be at least 80%.

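### Exclusion 23 states its white-cell and platelet limits per mL, so read literally these two numeric limits would exclude almost no one; the unit needs checking and correcting in both places

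*Combined protocol and SAP*

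**What the plan says.** Section 6.2 opens its list with an operative rule: "Candidates will be excluded from the study if any of the following conditions are present". Any single listed condition is therefore enough to exclude.

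Item 23 gives three laboratory limits in one line: "Leukopenia (WBC < 3000 cell/mL), anemia (Hgb < 9 g/dL), thrombocytopenia (Plt < 50,000 cell/mL". It then adds a limb without a number: "history of bleeding diathesis or coagulopathy or hypercoagulable states". Item 23 in the synopsis carries the same numerals and the same units.

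The counts come from the screening laboratory panel in Section 7.2, which lists "White blood cell count (WBC), Hemoglobin, Platelet count" and gives no unit. The other places that mention these counts are the post-procedure and discharge panels (Sections 7.4 and 7.5), Table 3, and the list of events that need not be reported (Section 8.3.1). None of them gives a unit or a numeric limit for white cells or platelets.

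**The concern.** The two cell-count limits are on a scale that does not match the conditions they are meant to define. Blood counts are usually reported per microlitre or as 10^9/L. This is general measurement knowledge and is not stated in the documents. Against that scale, a limit of a few thousand white cells or tens of thousands of platelets per mL describes blood with almost no cells. The hemoglobin limit in the same line, in g/dL, is on its usual scale, so the problem is confined to the two counts.

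The item is an eligibility rule for a procedure that involves arterial puncture (Section 7.3), heparin during the implant and antithrombotic treatment afterwards (Table 2). Someone checking eligibility against the printed text would find that a candidate with a markedly low count passes both numeric limits. Someone who mentally substitutes another unit applies a threshold that the protocol does not contain. In either case the written rule cannot be used to verify who should have been excluded.

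**Working it through.** **Inputs**

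- White-cell limit: "Leukopenia (WBC < 3000 cell/mL" (Section 6.2, item 23; same in the synopsis).
- Platelet limit: "thrombocytopenia (Plt < 50,000 cell/mL" (same places).
- Conversions: 1 mL = 1000 microlitres; 1 L = 1000 mL.

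The plan gives no derivation of these limits, so there is no calculation of its own to reproduce.

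**Step 1: the limits as printed**

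- White cells: 3000 per mL / 1000 = 3 per microlitre. In SI form, 3000 x 1000 = 3,000,000 per L = 0.003 x 10^9/L.
- Platelets: 50,000 per mL / 1000 = 50 per microlitre. In SI form, 50,000 x 1000 = 50,000,000 per L = 0.05 x 10^9/L.

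**Step 2: the same numerals read per microlitre**

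This step only measures the discrepancy; it does not propose a limit.

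- White cells: 3000 x 1,000,000 = 3.0 x 10^9/L.
- Platelets: 50,000 x 1,000,000 = 50 x 10^9/L.
- Ratio to the printed limits: 3.0 / 0.003 = 1000 and 50 / 0.05 = 1000.

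**Step 3: would low counts be caught by the printed limits?**

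The counts below are assumed for illustration and are not in the documents.

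| Count | Per microlitre | Per mL | Printed limit per mL | Excluded by the number? |
|---|---|---|---|---|
| White cells | 100 | 100,000 | 3000 | No |
| White cells | 1000 | 1,000,000 | 3000 | No |
| White cells | 2900 | 2,900,000 | 3000 | No |
| Platelets | 1000 | 1,000,000 | 50,000 | No |
| Platelets | 20,000 | 20,000,000 | 50,000 | No |
| Platelets | 49,000 | 49,000,000 | 50,000 | No |

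Even the lowest rows lie well above the limits: 100,000 / 3000 is about 33 times the white-cell limit, and 1,000,000 / 50,000 is 20 times the platelet limit.

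**Step 4: does anything else correct the unit?**

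No. The synopsis repeats it, and the screening, post-procedure, discharge, schedule and adverse-event sections give no unit for these counts.

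**Step 5: does it reach the statistics?**

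No. Section 10.2 says "The primary statistical analysis for this study is to estimate the procedure success rate". The sample-size statement there, the primary endpoint (Section 5.1) and the analysis populations (Section 10.1) do not use these limits.

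**The case against.** **The intent is obvious.** The limits sit beside the words leukopenia and thrombocytopenia, and any clinician would see that a near-zero count is not meant. This largely stands: sites and the Case Review Board would probably apply the usual scale. It does not make the printed rule correct. Section 12.7 bars investigators from departing from the protocol except in an emergency, and Section 12.6 allows changes only by written amendment, so the correction belongs with the sponsor.

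**Other safeguards exist.** The bleeding-diathesis limb of item 23 and item 24, on antithrombotic therapy, could catch some candidates with low platelets. A site surgeon must examine every subject (Section 7.2.1), and every case is reviewed and approved before the procedure (Sections 9.2.1 and 11.2). This also stands in part. These safeguards do not replace a numeric limit, and neither of those two exclusions directly addresses a low white-cell count.

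**It may be a reading fault.** The disputed character is a single letter, where a micro sign would be expected. The microlitre appears nowhere else in the document, so whether that sign survives conversion from PDF cannot be tested. Section 6.2 also has a one-letter slip in the word for a single-cusp valve that the synopsis does not share, and its origin is unknown. On the other side, both copies of item 23 agree, although one systematic misreading would also produce that, and symbols such as plus-minus (Section 7.8) and the degree sign (Section 8.3.1) came through. A fault is unproven but possible, so the source file should be checked first.

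**Stronger readings that the documents do not support.** A reader might infer that patients with marked cytopenia will be enrolled in numbers. The recognisable labels and case-by-case approval make that unlikely, and the number affected cannot be derived. A reader might also infer that excluding someone on the usual scale would be a protocol deviation. The documents do not show this: meeting the written criteria does not guarantee entry, and the Board may weigh other relevant clinical factors. Nor do they describe an automated eligibility check in the data-capture system or a Case Review checklist that would apply the number mechanically.

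**Conclusion.** The point holds as a unit error in an operative eligibility criterion, present in both places where the criterion appears and corrected nowhere. As printed, the two count limits are 3 white cells and 50 platelets per microlitre, which contradicts the criterion's own labels and would exclude almost no one on the numbers alone. The factor of 1000 rests on the assumption that the numerals were meant per microlitre, which only the sponsor can confirm. The existence of the error also assumes that the text matches the source PDF.

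The realistic consequence is an eligibility rule that is ambiguous and cannot be verified as written. Widespread misenrolment is unlikely. The hemoglobin limit and the qualitative limb of item 23 still work as written. The primary endpoint, sample size and analysis populations are untouched. The correction is worth making because the rule guards entry to an invasive procedure and the change is small.

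**What to change.** 1. Check the unit in item 23 against the source PDF, in Section 6.2 and in the synopsis. If the source already shows a different unit, the point falls away.
2. If the source reads per mL, have the sponsor confirm the intended unit and values for white cells and platelets. No limit is proposed here.
3. Correct the volume unit identically in both places at the next amendment. If any site or data-capture form repeats the limit, it should carry the same correction; the documents do not show that one does.

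The cost is a two-place text edit. The sample size, visit schedule and analysis do not change.

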## 7 STUDY PROCEDURES

### 7.1 Informed Consent

The study investigator(s) and support staff will approach subjects with symptomatic, severe calcific AS who meet general requirements to assess their interest in participating in the study by providing them an overview of the study including the background, risks, benefits and study procedures. If subjects are interested in participating in the study, the subject will sign the IRB/EC-approved informed consent form (ICF) prior to any study-specific procedures being performed. All subjects consented should be entered into the study's Electronic Data Capture (EDC) system. Subjects will be considered enrolled once the subject signs and dates the ICF.

### 7.2 Screening

The screening assessments will be completed within 30 days prior to the valve implant procedure, unless otherwise noted. Screening assessments will include the following:

#### Systems:

- Medical History

- Physical Assessment (height, weight, blood pressure and heart rate only)
- Medications: Antithrombotics (anticoagulants, antiplatelets, thrombolytics) only

**Risk:**

- STS Risk Score
- EuroSCORE II

**Cardiopulmonary:**

- NYHA Functional Class
- 12-lead Electrocardiogram (ECG)
- Transthoracic Echocardiogram (TTE) – Qualifying TTE must be performed within 90 days prior to the valve implant procedure.
- Cardiac CT Angiography (CTA) with 3D reconstruction to determine aortic annulus area. Qualifying cardiac imaging must be performed within 1 year prior to the valve implant procedure.
- Iliofemoral CTA, including thoracic and abdominal scan with visualization of iliac and femoral arteries. Iliofemoral CTA must be performed within 1 year prior to the valve implant procedure.
- Assessment of severity of coronary artery disease (CAD) may be performed by CTA or coronary angiography. If CTA shows evidence or high likelihood of obstructive CAD or if the CTA is non-diagnostic, coronary angiography must be performed to assess the need for intervention. Qualifying CTA/coronary angiography must be performed within 1 year prior to the valve implant procedure.
- Pulmonary Function Test – only for subjects with a history of lung disease
- SYNTAX Score – only for subjects with significant native CAD

**Neurological:**

- Modified Rankin Scale (mRS)

**Clinical Laboratory Tests:**

- White blood cell count (WBC), Hemoglobin, Platelet count
- Prothrombin Time (PT) or International Normalized Ratio (INR)
- Creatine Kinase (CK) and/or Troponins  $\leq$  72 hours before the valve implant procedure
- Creatinine (including calculation of eGFR per the Cockcroft-Gault formula)
- Albumin (as part of Frailty Index), total bilirubin
- Aspartate Aminotransferase (AST), Alanine Aminotransferase (ALT) – only for subjects with chronic liver disease
- Pregnancy test (urine or serum) – only for female subjects of childbearing potential

**Functional:**

- Frailty Index (5 Meter Walk Test, grip strength, Activities of Daily Living and serum Albumin)

### **7.2.1 Case Review**

Before a case is submitted for review, study site personnel will screen the subject for general enrollment criteria and ensure that the subject has been entered into the EDC System. It is required that at least one site surgeon Investigator personally examine the subject to determine operative risk. Once fully screened and deemed an appropriate candidate, the site will submit the case for consideration by the Case Review Board. If the case is approved, the subject may be scheduled for the valve implant procedure. If the case is not approved, the subject's status will be terminated.

Edwards will maintain a record of the case presentation and case approval notes.

### **7.3 Procedure**

The study devices will be used per the most current IFU for device sizing, preparation and recommended implant procedure. Only physicians appropriately trained to the use of the device and identified on the Delegation of Authority (DoA) log on file with Edwards may perform the implant procedure in study subjects.

The valve implant procedure will be considered to have started when the first interventional access-related puncture (arterial) is established. It is strongly encouraged that the procedure be performed within 14 days of Case Review Board approval.

Procedure assessments will include the following:

**Systems:**

- Medications: Antithrombotics only
- Adverse Events

**Cardiopulmonary:**

- Aortogram to assess valve placement
- Assessment of PVL by either:
  - TEE, or
  - Limited TTE and Aortogram

If the procedure is aborted (prior to or after the start of the valve implant procedure), the procedure may be re-scheduled if the subject continues to meet all eligibility criteria.

### 7.3.1 Antithrombotic Recommendations

**Table 2** outlines the recommended antithrombotic regimen.

**Table 2: Recommended Antithrombotic Regimen**

Pre-Valve Implant Procedure	
 
Aspirin (ASA) 81-100 mg QD
 

	
 
Subjects with a bare metal stent (BMS) within one month or drug-eluting stent (DES) within 12 months should be continued on Clopidogrel/prasugrel prior to their implant procedure.
 
Subjects in atrial fibrillation on warfarin should be bridged with low molecular weight (LMW) or unfractionated (UF) heparin prior to the implant procedure.
 
Subjects with persistent or paroxysmal atrial fibrillation and not on anticoagulation will not be required to have a TEE to rule out left atrial (LA) thrombus prior to implant procedure. If intra-procedural TEE during TAVR reveals thrombus, implant procedure will be aborted and delayed until subject has been on warfarin or dabigatran for 30 days. Note: thrombus must be eliminated in order to proceed with TAVR.
 
In subjects undergoing concomitant TAVR/Percutaneous Coronary Intervention (PCI), Clopidogrel loading with either 300 mg or 600 mg prior to the implant procedure is recommended in addition to ASA.
 

Intraprocedural	
 
Heparin will be given to achieve/ maintain activated clotting time (ACT) <math>\geq</math> 250 sec.
 

Post-Valve Implant Procedure	
Category I for Stroke Risk: No atrial fibrillation, no recent stents
 
 
ASA 81 mg QD
 
Clopidogrel 300 mg load within 6 hours of the implant procedure (either pre or post)
 
Clopidogrel 75 mg QD for at least one month post-implant procedure
 
 
Category II for Stroke Risk: No atrial fibrillation, recent stents
 
 
ASA 81 mg QD
 
Clopidogrel 75 mg QD should be continued after the implant procedure without interruption for at least one month post-BMS and 12 months post-DES
 
 
Category III for Stroke Risk: Atrial fibrillation, no recent stents
 
 
ASA 81 mg QD
 
Subjects should be started on warfarin or dabigatran 24 hours post-TAVR if clinically safe and this should be continued for at least one month or indefinitely, if possible. If clinically safe, subjects started on warfarin should be bridged with UF or LMW heparin until INR therapeutic.
 
If subjects are not a candidate for warfarin or dagibatran, Clopidogrel 75 mg QD can be considered as an alternative.
 
 
Category IV for Stroke Risk: Atrial fibrillation, recent stents
 
 
ASA 81 mg QD
 
Clopidogrel 75 mg QD for at least one month post-BMS or 12 months post-DES
 
Subjects should be started on warfarin or dabigatran 24 hours post-TAVR if clinically safe and continued indefinitely. If clinically safe, subject's being started on warfarin should be bridged with UF or LMW heparin until INR therapeutic.
 

Note: Any changes to antithrombotic regimen from study visit to study visit will be noted on the electronic Case Report Form (eCRF) including reason for change.

### **7.3.2 Antibiotic Prophylaxis**

Study subjects should be prophylactically treated to prevent endocarditis per the recommendations of the AHA (22).

### **7.3.3 Contrast Media**

Careful management of contrast media is required. Accurate measurement of the contrast used will be captured in the subject medical records.

### **7.3.4 Radiation Precautions**

Radiation precautions will be adhered to per institutional standards. If a radiation-induced skin injury is suspected, the Investigator must report an adverse event, and assess and treat the subject as medically necessary.

## **7.4 Post-procedure**

The post-procedure time period is defined as the 48 hours after the subject exits the procedure room. The following will be assessed during the post-procedure time period:

### **Systems:**

- Medications: Antithrombotics only
- Adverse Events

### **Cardiopulmonary:**

- 12-lead ECG

### **Clinical Laboratory Tests:**

- WBC, Hgb, and platelet count
- PT or INR
- Creatinine

## **7.5 Discharge**

Discharge is the actual date and time the subject is discharged. For subjects discharged within 48 hours of exiting the procedure room, it is not required to repeat tests collected during the Post-Procedure period that are also required for the discharge visit. If the subject was discharged over a weekend or holiday, the discharge assessments may be completed on the last weekday prior to discharge.

The following assessments will be conducted within 24 hours of the date and time of discharge.

### **Systems:**

- Physical assessment (weight, blood pressure and heart rate only)

- Medications: Antithrombotics only
- Adverse Events

**Cardiopulmonary:**

- NYHA functional class
- TTE

**Clinical Laboratory Tests:**

- WBC, Hgb, and platelet count
- PT or INR
- Creatinine

**7.6 Follow-up**

The day of the procedure is considered Day 0 and will be used to schedule all subsequent visits and calculate visit windows. Six months is defined as 180 days; one year is defined as 365 days.

**7.6.1 30 Days**

The following assessments will be conducted at 30 days (+7 days):

**Systems:**

- Physical assessment (weight, blood pressure and heart rate only)
- Medications: Antithrombotics only
- Adverse Events

**Cardiopulmonary:**

- NYHA functional class
- TTE

